5 SUMMARY OF CHANGES

1. Updated the pharmacovigilance email address.
2. Updated the approximate number of study centers from 45 to 60.
3. Updated the Schedule of Events to include: a) footnote “e” (positive urine test after randomization confirmed by serum pregnancy test) and b) footnote “f”(autoantibody testing at screening).
4. Added new inclusion criterion #8, and removed original inclusion criteria # 8 and # 9 in [Section 13.1](#).
5. Updated the reporting of adverse events for physical examinations done between screening and randomization in [Section 19.4](#).
6. Updated clinical laboratory tests in [Section 19.7](#).
7. Updated subject withdrawal criteria in [Section 23.1](#).

6 ABBREVIATIONS

Abbreviation	Term
2x/week	Twice a week
ACTH	Adrenocorticotrophic hormone
AE	Adverse event
ALT	Alanine aminotransferase
ANC	Absolute neutrophil count
AST	Aspartate aminotransferase
BAFF	B cell activity factor
BILAG-2004	British Isles Lupus Assessment Group-2004
CFR	Code of Federal Regulations
CLASI	Cutaneous Lupus Erythematosus Disease Area and Severity Score
CNS	Central nervous system
CTX-I	C-terminal crosslinking telopeptide of Type I collagen
ECG	Electrocardiogram
eCRF	Electronic case report form
FDA	Food and Drug Administration
HbA1c	Glycosylated hemoglobin
HBsAg	Hepatitis B surface antigen
HBcAb	Hepatitis B core antibody
HCV	Hepatitis C virus antibody
HCV PCR	Hepatitis C virus polymerase chain reaction
HIPAA	Health Insurance Portability and Accountability Act
hSLEDAI	Hybrid Systemic Lupus Erythematosus Disease Activity Index
ICF	Informed consent form
ICH	International Council for Harmonisation
ID	Identification
IEC	Independent Ethics Committee
IFN-alpha	Interferon alpha
Ig	Immunoglobulin
IGRA	Interferon gamma release assay
IL	Interleukin
IMP	Investigational medicinal product
IRB	Institutional Review Board
IV	Intravenous, intravenously
IXRS	Interactive Phone/Web Response System
MCR	Melanocortin receptor
mITT	Modified intent-to-treat
MM	Medical monitor
NSAID	Nonsteroidal anti-inflammatory drugs
PGA	Physician's Global Assessment
PINP	N-terminal propeptide of Type I collagen

Abbreviation	Term
QOL	Quality of life
SAE	Serious adverse event
SC	Subcutaneous, subcutaneously
SELENA	Safety of Estrogens in Lupus Erythematosus National Assessment
SFI	SELENA Flare Index
SLE	Systemic Lupus Erythematosus
SLEDAI-2K	Systemic Lupus Erythematosus Disease Activity Index-2000
SRI	Systemic Lupus Erythematosus Responder Index
sVCAM-1	Soluble vascular cell adhesion molecule-1
TB	Tuberculosis
TEAE	Treatment-emergent adverse event
U	Unit(s)
US	United States
ULN	Upper limit of normal
WPAI	Work Productivity and Activity Impairment Questionnaire

Mallinckrodt

[figure not shown]
Study Title: A Multicenter, Randomized, Double Blind, Placebo Controlled Study to Assess the Efficacy and Safety of Acthar® Gel in Subjects With Persistently Active Systemic Lupus Erythematosus Despite Moderate Dose Corticosteroids	
Protocol Number: MNK14304067	Type: Phase 4 (US)/ Phase 2 (Outside the US)
Condition/Disease:	Systemic Lupus Erythematosus

and randomization), and a BILAG-2004 score of A or B in the in the mucocutaneous and/or musculoskeletal body systems at screening and randomization. Subjects must have a documented history of a positive antinuclear antibody (ANA) or a screening result of a positive ANA test by immunofluorescent assay (IFA) with a titer $\geq 1:80$ or an equivalent assay; or a documented history or positive screening result of elevated anti-dsDNA or ENA antibodies (e.g., anti-Smith, SSA, SSB, RNP).. Subjects with Type 1 or Type 2 diabetes, active central nervous system manifestations of SLE or active lupus nephritis, tuberculosis, history of hepatitis, peptic ulcer, active infection, or any contraindication for Acthar will be excluded. Subjects must exhibit disease activity despite being on a stable daily dose of a corticosteroid (7.5 mg to 30 mg per day [inclusive] of prednisone or prednisone equivalent) for at least 4 weeks prior to the Screening Visit.
 
Subjects may be taking antimalarials and nonsteroidal anti-inflammatory drugs if they are on a stable dose for at least 4 weeks prior to the Screening Visit and will remain on that dose throughout the study. Subjects may be taking methotrexate, azathioprine, and/or mycophenolate mofetil if they are on a stable dose for at least 8 weeks prior to the Screening Visit and will remain on that dose throughout the study. Subjects must not have received any steroid injection (intramuscular, intraarticular, or intravenous) within the 4 weeks prior to the Screening Visit. Subjects must not have received cyclosporine, oral corticosteroid doses > 30 mg per day of prednisone or equivalent, or any non-biologic investigational drug within the 3 months prior to the Screening Visit. Subjects must not have received intravenous immunoglobulin or plasmapheresis within the 4 months prior to the Screening Visit. Subjects must not have received cyclophosphamide, abatacept, B cell targeted therapies (anti-CD-22 agents [epratuzumab] or belimumab), B cell depleting therapy (rituximab or other anti-CD20 agents, or anti-CD52 agents [alemtuzumab]), or any biologic investigational agent within the 6 months prior screening.
	

Concomitant Medications and Treatments:
 
Subjects must remain on stable daily dose of prednisone or prednisone equivalent through Week 16 of the study. Taper of corticosteroid is encouraged between Weeks 16 and 24 as clinically indicated.
 
All other background medications for SLE must remain stable throughout the study.
 
No new immunosuppressant therapies or other new treatments for SLE may be initiated during the study.
 
Subjects are not permitted to receive live or live-attenuated vaccines during the study.
 
All medications and nondrug therapies (eg, blood transfusions, oxygen supplementation) taken from 30 days prior to the Screening Visit and throughout the study will be recorded.
	

Study Drug and Treatment Administration:
 
Acthar is a sterile preparation of purified adrenocorticotrophic hormone (ACTH) analogue formulated in a gel for repository administration. Acthar and its matching placebo will be supplied by the sponsor and administered SC as follows in this study:
 
Treatment A: Acthar 1 mL (80 U) administered SC every other day from Week 0 to 4 and 2x/week from Weeks 5 to 24.
 
Treatment B: Placebo 1 mL administered SC every other day from Week 0 to 4 and 2x/week from Weeks 5 to 24.
	

Efficacy Evaluations:
 
The following efficacy assessments will be evaluated: SRI, SLEDAI-2K, BILAG-2004, PGA, Safety of Estrogens in Lupus Erythematosus National Assessment (SELENA) Flare Index (SFI), Cutaneous Lupus Erythematosus Disease Area and Severity Score (CLASI), 28 Joint Count, and prednisone usage after Week 16.
	

Study Title: A Multicenter, Randomized, Double Blind, Placebo Controlled Study to Assess the Efficacy and Safety of Acthar® Gel in Subjects With Persistently Active Systemic Lupus Erythematosus Despite Moderate Dose Corticosteroids	
Protocol Number: MNK14304067	Type: Phase 4 (US)/ Phase 2 (Outside the US)
Condition/Disease:	Systemic Lupus Erythematosus

group as a factor and the baseline value of the corresponding endpoint as a covariate. Mixed model with repeated measurements will be performed as deemed necessary. Secondary and exploratory endpoints that are proportions will be analyzed using Pearson's chi-square test or Fisher's exact tests.
 
[REDACTED]
 
[REDACTED]
 
[REDACTED]
 
[REDACTED]
 
[REDACTED]
 
[REDACTED]
 
[REDACTED]
	

Safety Analysis
 
Treatment-emergent adverse events and serious adverse events will be summarized using the MedDRA by preferred term within system organ class.
 
Hospital admissions and the reason for each admission will be listed and summarized descriptively by visit and treatment. The cumulative number of hospital admissions will be compared between treatment groups at Week 24 with a 2-sided Pearson's chi-square test or Fisher's exact test at a significance level of 0.05.
 
Other safety data will be listed and summarized descriptively or graphically, as appropriate.
 
[REDACTED]
 
[REDACTED]
 
[REDACTED]
 
[REDACTED]
	

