13 SELECTION OF SUBJECTS

13.1 Inclusion Criteria

Subjects must meet all of the following criteria for inclusion in the study at the Screening Visit and the Randomization Visit.

1. Subjects must be adequately informed and understand the nature and risks of the study and must be able to provide a signature and date on the ICF.
2. Subjects must be ≥ 18 years of age at Screening Visit and can be male or female.
3. Female subjects must be of nonchildbearing potential (history of hysterectomy, bilateral oophorectomy, or bilateral tubal ligation; or postmenopausal with no history of menstrual flow in the 12 months prior to the Screening Visit); or if of childbearing potential must be nonpregnant, nonlactating and agree to use effective contraception when with a male partner throughout study participation (through the Follow-up Visit). Acceptable forms of contraception include hormonal measures (oral contraceptive pills, contraceptive patch, contraceptive ring, injections), intrauterine devices, double barrier method (condom plus diaphragm, condom or diaphragm plus spermicidal gel or foam), and abstinence.
4. Male subjects with a female partner of childbearing potential must have been surgically sterilized (vasectomy) or agree to use a double barrier for contraception (condom plus

- diaphragm, condom or diaphragm plus spermicidal gel or foam) or remain abstinent throughout their study participation (through the Follow-up Visit).
5. Subjects must have a diagnosis of SLE according to the American College of Rheumatology revised criteria (fulfilled ≥ 4 criteria) ([Hochberg, 1997](#); [Tan et al, 1982](#)).
 6. Subjects must have active SLE as demonstrated by a SLEDAI-2K score of ≥ 6 at the Screening Visit and a clinical SLEDAI (excluding laboratory results) score ≥ 4 at the Screening and Randomization Visits. Points for arthritis and/or rash must be present at both the Screening and Randomization Visits.
 7. Subjects must have moderate to severe rash and/or arthritis as demonstrated by BILAG-2004 score A or B in the in the mucocutaneous and/or musculoskeletal body systems at both Screening and Randomization Visits.
 8. A documented history of positive antinuclear antibody (ANA)
OR
A screening result of positive ANA test by immunofluorescent assay (IFA) with titer $\geq 1:80$ or an equivalent assay
OR
A documented history or positive screening result of elevated anti-dsDNA or ENA antibodies (e.g., anti-Smith, SSA, SSB, RNP).

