15.1 Screening Visit (Study Days -28 to -1) Procedures

Screening assessments must be performed within 1 to 28 days prior to the Week 0 Visit.

The following procedures will be performed at the Screening Visit:

- Informed consent.
- Inclusion/exclusion criteria.
- SLEDAI-2K and BILAG-2004.
- Medical and surgical history, including the first day of the last menstrual period for women of childbearing potential.
- Demographics.
- Complete physical examination.
- Height and Weight.
- Vital signs.
- 12-lead electrocardiogram (ECG).
- Clinical laboratory tests (chemistry, hematology, and urinalysis).
- Lipid panel.
- HbA1c.
- Serum pregnancy test.
- Hepatitis serology.
- IGRA test for TB.

- C3, C4 and anti-ds DNA antibodies.
- Serology (ANA, ENA; if history is unavailable)
- Contact the Interactive Phone/Web Response System (IXRS).
- Adverse events and concomitant medications.

Subjects will be allowed to repeat any screening procedure once, if necessary, if it is within the screening window.

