15.2 Randomization Visit (Week 0) and First Dose Procedures

All evaluations will occur prior to the first dose of study drug, except as noted.

- Inclusion/exclusion criteria review.
- [REDACTED]
- [REDACTED]
- 28 Joint Count, SLEDAI-2K, BILAG-2004, PGA, and CLASI -Activity.
- Current medical condition review.
- Limited physical examination.
- Weight.
- Vital signs.
- Clinical laboratory tests.
- Lipid panel.
- Urine pregnancy test.
- C3, C4, and anti-ds DNA antibodies.
- [REDACTED]
- [REDACTED]
- [REDACTED]
- [REDACTED]
- Subject diary and study drug administration training.
- Contact IXRS and dispense study drug kits.

- Study drug administration under supervision of study staff and observation for at least 1 hour thereafter.
- Adverse events and concomitant medications.

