21.3.2 Secondary Efficacy Endpoints

- Change from baseline over time in SLEDAI-2K (Week 0 to 16).
- Time to first response as assessed by SRI.
- Change from baseline over time in total BILAG-2004 (Week 0 to 16).
- Change from baseline over time in PGA (Week 0 to 16).
- Proportion of subjects with decrease from baseline of ≥ 4 points in SLEDAI-2K over time (Week 0 to 16).
- Change from baseline in CLASI-Activity score over time (Week 0 to 16) in subjects with CLASI-Activity at baseline.
- Change from baseline (Week 0 to 16) in 28 Joint Count (tender and swollen) in subjects with tender and swollen joints at baseline.

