21.6 Efficacy Analysis

Subjects will be included in the efficacy analyses based on their treatment assignment. The primary endpoint is the proportion of SRI responders at Week 16. The proportions of SRI responders for the 2 treatment groups will be summarized descriptively by visit and treatment group in tabular format and compared using a 2-sided Pearson's chi-square test at a significance level of 0.05. If the responder or nonresponder count falls to equal or below 5 in either treatment group, 2-sided Fisher's exact test will be used instead. All quantitative secondary and exploratory endpoints will be analyzed using analysis of covariance models with treatment group as a factor and the baseline value of the corresponding endpoint as a covariate. Mixed model with repeated measurement will be performed as deemed necessary. Secondary and exploratory endpoints that are proportions will be analyzed using Pearson's chi-square test or Fisher's exact tests.

For the primary efficacy endpoint, subjects who do not provide data to allow classification as responders will be considered nonresponders, that is, missing data will be imputed as non-responder. A similar approach will be applied to secondary efficacy endpoints that are proportions; missing will be classified as not satisfying the conditions described for that endpoint. A full description of missing data imputation method for all endpoints will be described in the statistical analysis plan.

██
██
██
██
██
██

All subjects who receive at least 1 dose of study drug will be included in the safety analyses.

Adverse events will be coded using MedDRA (version 19.0 or higher) by preferred term within system organ class. The number of AEs and the number of subjects reporting AEs will be listed and summarized descriptively by body system, preferred term, severity, and causality for each treatment group. Only TEAEs (events that are new in onset or aggravated in severity following treatment) will be included in all summaries. SAEs (including death) will be summarized.

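### Optional improvement: the ANCOVA for change in SLEDAI-2K and total BILAG-2004 is valid, but adding the Screening score as a second covariate would probably gain a little precision at almost no cost

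*Combined protocol and SAP*

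**What the plan says.** Section 21.6 analyses all quantitative secondary and exploratory endpoints with "analysis of covariance models with treatment group as a factor and the baseline value of the corresponding endpoint as a covariate", and the synopsis likewise takes treatment "group as a factor and the baseline value of the corresponding endpoint as a covariate". A mixed model for repeated measurements is optional, and its covariates are not named.

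The two endpoints at issue are in Section 21.3.2: "Change from baseline over time in SLEDAI-2K (Week 0 to 16") and "Change from baseline over time in total BILAG-2004 (Week 0 to 16"). The visible text has no formal definition of baseline. The Week 0 to 16 label implies that it is the Week 0 score.

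Both indices are scored twice before the first dose. Section 15.1 lists "SLEDAI-2K and BILAG-2004" at Screening, and Section 15.2 lists "28 Joint Count, SLEDAI-2K, BILAG-2004, PGA, and CLASI -Activity" at the Randomization Visit. Table 8-1 agrees. On timing, Section 15.1 says: "Screening assessments must be performed within 1 to 28 days prior to the Week 0 Visit". Inclusion criterion 6 requires a "SLEDAI-2K score of ≥ 6 at the Screening Visit" and a clinical SLEDAI threshold at both visits. Criterion 7 requires a BILAG-2004 grade at both visits. Every eligible randomized subject should therefore have both scores.

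**The concern.** A single score of a fluctuating index is a noisy measure of a subject's usual level. A second pre-treatment score can carry information about the Week 16 value that the Week 0 score lacks. No efficacy model in the visible text uses the Screening score, so its only visible role is to decide eligibility.

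The stake is precision on the first and third listed secondary endpoints. Intervals may be somewhat wider than the collected data require. The Screening score precedes randomization and so is independent of assigned treatment, which means that adjusting for it introduces no bias.

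**Working it through.** **1. The plan's own power figure.** Section 21.11 gives 80 per arm, 30% against 55%, and 0.05. Section 21.6 makes the test two-sided. The pooled rate is 0.425.
- SE under the null: √(2 × 0.425 × 0.575 / 80) = 0.0782.
- SE under the alternative: √((0.30 × 0.70 + 0.55 × 0.45) / 80) = 0.0756.
- Power: Φ((0.25 − 1.96 × 0.0782) / 0.0756) = Φ(1.28) = 0.90.

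The stated 90% reproduces. It belongs to the unadjusted primary SRI comparison, which this point does not touch. The visible text gives no power figure for a secondary endpoint.

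**2. Formula for the gain.** Let r_b be the correlation of Week 0 with Week 16, r_s that of Screening with Week 16, and r_sb that of Screening with Week 0. Adding Screening removes the following fraction of the residual variance:

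g = (r_s − r_b·r_sb)² / [(1 − r_b²)(1 − r_sb²)]

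The documents give none of these correlations, so every value below is an assumption.

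| r_b | r_s | r_sb | Calculation | g |
|---|---|---|---|---|
| 0.50 | 0.50 | 0.50 | 0.0625 / 0.5625 | 11.1% |
| 0.50 | 0.50 | 0.70 | 0.0225 / 0.3825 | 5.9% |
| 0.50 | 0.50 | 0.80 | 0.0100 / 0.2700 | 3.7% |
| 0.50 | 0.50 | 0.90 | 0.0025 / 0.1425 | 1.8% |
| 0.50 | 0.45 | 0.75 | 0.005625 / 0.328125 | 1.7% |
| 0.50 | 0.40 | 0.80 | 0 / 0.2700 | 0% |
| 0.70 | 0.70 | 0.80 | 0.0196 / 0.1836 | 10.7% |

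The last two rows share r_sb = 0.80, so a high correlation between the two pre-dose scores does not by itself remove the gain. What counts is whether Screening predicts Week 16 beyond Week 0.

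**3. Cost of the extra covariate.** At N = 160, one more covariate inflates the variance by about 156/155 = 1.0065. If g = 0, the net loss is about 0.65%.

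**4. Entry thresholds.** Selection on the scores weakens the correlations, so the gain was also simulated with cuts of 6 at Screening and 4 at Week 0. The clinical SLEDAI rule was approximated on the total score. The assumed model is a stable subject level plus a decaying fluctuation plus rating error. Assumed inputs:
- mean score 8 or 10
- between-subject SD 3 or 4
- fluctuation SD 2 or 3
- decay time 7 or 30 days
- rating-error SD 0 or 1

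Reduction in residual variance:
- Gap of 14 to 27 days: about 2.5% to 16%.
- Gap of 3 days: about 0.7% to 7%.

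A second simulation set the correlations directly (mean 8 or 10, SD 4, the same cuts). With r_b = r_s = 0.5 and r_sb from 0.5 to 0.7 before selection, the reduction was 4% to 8%. In the cases with a weaker Screening correlation it was 0% to 0.8%.

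**5. What this means in practice.** A reduction g is worth 160/(1 − g) subjects: 160/0.99 = 162, 160/0.95 = 168, 160/0.90 = 178, 160/0.85 = 188. For a hypothetical comparison with 80% power, the new power is Φ(2.80/√(1 − g) − 1.96), which is about 80.3%, 82%, 84% and 86% for g = 1%, 5%, 10% and 15%.

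**The case against.** The strongest reply is that nothing in the plan is wrong. ANCOVA on treatment and the endpoint's own baseline is valid and unbiased under randomization. A reader might infer that the plan contains an analysis error, or that precision is certainly lost. The documents support neither. They give no SD or correlation for either index, and if the disease process decays without a persistent subject level or rating error (r_s = r_b·r_sb), the gain is exactly zero. The simulated gains depend on assuming that such a level persists to Week 16. That is plausible for persistently active disease with corticosteroid doses held stable through Week 16, but it is not shown.

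Four further limits stand:
- The calculations are modelled on SLEDAI-2K. Under Section 17.1.2, BILAG-2004 compares the last four weeks with the four before, so the recall windows of the two visits overlap whenever the gap is under 28 days. The two scores may then be partly redundant.
- The Screening visit may be as little as one day before Week 0, and shorter gaps give smaller gains.
- Week 0 as the baseline is an inference. The opening of Section 21.1 is not in the available text, and redacted lines follow the efficacy analysis, so a definition may exist there.
- Sections 13.3 and 15.1 allow a screening assessment to be repeated once, and 13.3 allows one rescreening. A proposal that does not say which value counts would leave the analyst a choice.

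On the other side, the worst case is a loss of under 1%, and the data are collected anyway.

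**Conclusion.** This is a free improvement of optional severity. The visible ANCOVA is sound but uses one of two available pre-treatment scores. Adding the Screening score would probably cut residual variance by roughly 1% to 15% under models with a persistent subject level. The lower end applies to short gaps. The effect is zero, or a loss of about 0.65%, if Screening adds nothing beyond Week 0. These figures rest on assumed correlations and on SLEDAI-2K entry rules, and the gain for total BILAG-2004 is less certain.

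Two stronger inferences should be resisted. The point does not weaken the primary SRI test, the sample size or the 90% power, none of which uses this model. Nor is the Screening score wholly unused, since it decides eligibility.

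**What to change.** In Section 21.6 and the synopsis, prespecify before unblinding:

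> For change in SLEDAI-2K and total BILAG-2004, the ANCOVA (and any mixed model) will include treatment, the Week 0 score and the Screening score of the same endpoint. The Screening score is the last qualifying value before the Randomization Visit, including after a repeat or rescreening.

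State explicitly that baseline is the Week 0 score, and keep change from baseline defined from it. The cost is this text and one degree of freedom per model. No new data are needed. The timing matters because a covariate chosen after unblinding would be open to challenge.

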8 STUDY SCHEMATIC AND SCHEDULE OF EVENTS

8.1 Study Schematic

Figure 8-1: Study Overview

8.2 Schedule of Study Events

Table 8-1: Schedule of Study Events

Assessment/Procedure	Screening (Day-28 to Day -1)	Randomization	Dosing	Treatment Period								Follow-up
Week		0	0	2 (± 3 days)	4 (± 3 days)	6 (± 3 days)	8 (± 3 days)	12 (± 5 days)	16 (± 5 days)	20 (± 5 days)	24 (± 5 days)/Early Termination	28 (± 5 days)
Informed Consent	X											
Inclusion/Exclusion Criteria Review	X	X										
Demographics	X											
Medical/Surgical History	X											
Current Medical Condition Review		X		X	X	X	X	X	X	X	X	X
Complete Physical Examination	X										X	
Limited Physical Examination		X		X	X	X	X	X	X	X		X
Height and Weight ^a	X	X		X	X	X	X	X	X	X	X	X
Vital Signs ^b	X	X		X	X	X	X	X	X	X	X	X
12-lead ECG	X										X	
Clinical Laboratory Tests ^c	X	X		X	X	X	X	X	X	X	X	X
Lipid Panel	X	X						X			X	
HbA1c	X							X			X	
Serum Pregnancy Test	X										X	
Urine Pregnancy Test ^d		X					X		X			X
IGRA for TB	X											
Hepatitis Serology ^c	X											
		X						X			X	
C3, C4 and anti-ds DNA antibodies	X	X		X	X	X	X	X	X	X	X	
Serology (ANA, ENA) ^f	X											

Assessment/Procedure	Screening (Day-28 to Day -1)	Randomization	Dosing	Treatment Period								Follow-up
Week		0	0	2 (± 3 days)	4 (± 3 days)	6 (± 3 days)	8 (± 3 days)	12 (± 5 days)	16 (± 5 days)	20 (± 5 days)	24 (± 5 days)/Early Termination	28 (± 5 days)
		X					X		X		X	
		X					X		X		X	
		X					X		X		X	
SLEDAI-2K	X	X		X	X	X	X	X	X	X	X	
BILAG-2004	X	X			X		X	X	X	X	X	
PGA		X			X		X	X	X	X	X	
SFI					X		X	X	X	X	X	
CLASI-Activity		X			X		X	X	X	X	X	
28 Joint Count		X			X		X	X	X	X	X	
		X					X		X		X	
		X					X		X		X	
Hospital Admissions				X	X	X	X	X	X	X	X	
IXRS Contact	X	X		X	X	X	X	X	X	X	X	
Study Drug and Diary Training		X										
Study Drug Accountability and Diary Review				X	X	X	X	X	X	X	X	
Dispense Study Drug and Diary		X		X	X	X	X	X	X	X		
Administer First Dose			X									
Adverse Events and Concomitant Treatments								X				

^aHeight at screening only.

^bBlood pressure, respiratory rate, pulse rate and body temperature. For blood pressure, an average of 3 readings after the subject has been seated for ≥ 5 minutes at The Screening and Randomization Visits. Single readings after subject has been seated for ≥ 5 minutes at all other time points.

^cChemistry, hematology assays, and urinalysis (see Attachment 1).

^dPositive urine test after randomization will be confirmed by serum pregnancy test.

^eHepatitis B surface antigen, Hepatitis B core antibody (HBcAb), hepatitis C virus antibody (HCV Ab), hepatitis C polymerase chain reaction([HCV PCR] for subjects positive for HCV Ab only).

^fAutoantibody testing (ANA, ENA) may be performed if history is unavailable.

